**Specific Aim 2. To determine if OSA improves in women with PCOS treated with estrogen or progesterone.** For these studies, we will enroll women with PCOS who have OSA. Subjects will have a detailed baseline metabolic and metabolomic profile together with a baseline polysomnogram. Subjects will then receive a single dose of depot-leuprolide in order to suppress ovarian production of estrogen, progestin, and androgen over a period of 3 months. Six weeks after administration of depot-leuprolide, subjects will have repeated assessment of metabolic, metabolomic, and sleep measures to determine if these outcomes are altered by the combined suppression of ovarian sex steroids. Subsequently, subjects will be randomized in a double-blind placebo controlled fashion to one of two treatment arms for a period of six weeks. Treatment arms are: estrogen plus placebo or progesterone plus placebo. At the end of this second six weeks, subjects will have metabolic, metabolomic, and sleep measures repeated. Primary outcome measures will be compared both within and between treatment arms.

**Specific Aim 3. To determine if metabolic disturbances present in PCOS women with OSA are ameliorated by the treatment of OSA with continuous positive airway pressure (CPAP).** The presence of OSA in women with PCOS has a significant negative effect upon metabolic measures. In particular, the presence of OSA in PCOS is associated with hyperinsulinemia, elevations in plasma glucose, and lipid abnormalities that include higher levels of triglycerides and LDL-cholesterol. OSA in PCOS is also associated with hypercortisolemia that persists throughout both day and night. Results of our preliminary studies indicate that CPAP treatment of OSA results in attenuation of cortisol levels not only during sleep, but throughout waking hours as well. This aim will serve to test the hypothesis that correction of OSA in PCOS will lead to improved metabolic function which can be attributed, at least in part, to a reduction in circulating levels of cortisol.

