**At 15:50, a GnRH agonist test will be performed, as depicted in FIGURE D2-3 below.**

At 15:50, a 15cc blood sample for LH, FSH, estradiol, estrone, total and free testosterone, progesterone, 17-hydroxyprogesterone, and androstenedione will be obtained. At 15:59, a 5 cc blood sample will be taken for LH and FSH. At 16:00, leuprolide acetate 10 µg/kg will be given as a single subcutaneous injection. At 16:30, 17:00 and 20:00, 5 cc samples will be obtained for LH and FSH. A 15 cc sample will be obtained for estradiol, estrone, total and free testosterone, progesterone, 17-hydroxyprogesterone, and androstenedione after 16, 20, 24 hours GnRHa administration, i.e. at 8:00, 12:00 and 16:00.

As depicted in Figure D1-1, it is at this point that subjects will have completed the Screening and Specific Aim 1 Procedures. Details of procedures for subjects randomized into Specific Aim 2 or Specific Aim 3 are provided below.

### D3. Detail of methods pertaining to Specific Aims 2 and 3

The PCOS women with OSA studied in Aim 1 plus additionally enrolled PCOS women with OSA (for a total of 60 subjects) will be randomized in a ratio of 2:1 to participate in Aim 2 (n=40) or Aim 3 (n=20). Block randomization will be performed using computer-generated random numbers. The primary outcomes measure for Aim 2 is the AHI difference pre- and post-interventions, as detail in Section D3; the primary outcomes measure for Aim 3 is the change in 24 hr cortisol concentration pre- vs post-CPAP

Subjects randomized to Specific Aim 2 will have suppression of endogenous LH secretion, and thus ovarian sex-steroid production, by administration of a single intramuscular dose (11.25 mg) of the GnRH agonist depot leuprolide. Leuprolide is a synthetic nonapeptide analog of naturally occurring gonadotropin-releasing hormone (GnRH). The analog possesses greater potency than the natural hormone. When the depot form of leuprolide is administered at a dose of 11.25 mg, there is prolonged (3 month) suppression of pituitary gonadotropin levels and ovarian steroid levels as documented in the literature (115) and exemplified in Preliminary Studies. Six-weeks after administration, subjects will return to the GCRC for repeated evaluation, identical to that conducted at Baseline under Specific Aim 1.

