After this midpoint assessment, subjects will again enter into a randomized phase of the protocol. Subjects will be assigned to receive one of two treatment regimens in a randomized, double-blind, placebo controlled fashion, for a period of 6 weeks. Subjects will receive daily oral doses of either **2 mg micronized estradiol (Estrace®) plus placebo –OR– 200 mg micronized progesterone (Prometrium®) plus placebo.**

Rationale for preparation and dose of estrogen and progesterone. Natural estradiol is poorly absorbed in its native form and undergoes rapid metabolism in a first-pass effect through the liver. Thus, micronization (micronized estradiol) or acetylation (ethinyl estradiol) is required to achieve adequate blood hormone levels. Micronized estradiol is extremely well-absorbed and much of the compound is metabolized to estrone sulfate (65%) and estrone (15%). This “pool” of estrone and estrone sulfate then serves as the source of regenerated estradiol. At a dose of 2 mg per day, the steady-state levels of estradiol and estrone are typically 220 pmol/L and 68 pmol/L, respectively (116) and most closely recapitulate those seen in normal women in the midfollicular phase of the menstrual cycle (110). Because ethinyl estradiol is poorly converted to estrone, it will not be selected for use in these protocols. Micronized progesterone at a dose of 200 mg per day has been reported to result in attainment of serum progesterone concentrations typically seen in the late follicular/early luteal phase of the cycle (data provided by manufacturer).

Subjects randomized to Specific Aim 3 will be treated with nasal CPAP for a period of 6 weeks. Compliance will be documented based upon results provided by a microchip sensor that detects not only if the unit is powered on, but also if the mask is being worn by the subject. These data cannot be altered by the individual and there is no access to this microsensor by the user. The subjects who have OSA will undergo one night of CPAP titration study at the end of the baseline assessment. After 6 wks of home CPAP, the experimental study outline above will be repeated with CPAP use at night. Subjects whose average nightly CPAP use is > 5 hr will be considered compliant.

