**D4. Potential pitfalls and plans for their resolution**

re: Specific Aim 1. In studies conducted under Specific Aim 1, subjects will be recruited to participate in a wide variety of procedures over a number of weeks. Recruitment and retention may pose challenges, however we have longstanding experience with studies of this nature and our recruitment procedures have been successful to date; our retention rates in similar studies has been over 90%. Subjects are contacted on a regular basis by our study coordinator. Subjects also receive monetary compensation for participation in the protocols. We have successfully recruited subjects in the past through cooperation with other physicians who care for patients with PCOS and we plan to do so again in the event that recruitment goals are lagging.

re: Specific Aim 2. Studies in this Aim are anticipated to flow smoothly. Potential problems include drop-outs related to intolerance/untoward effects of study medication and lack of compliance. It is anticipated that additional subjects may need to be recruited to replace the drop-outs. Another potential pitfall is that the degree of testosterone suppression expected after depot-leuprolide administration may be insufficient (i.e., testosterone levels may remain above the normal female range). If this proves to be the case, we will use testosterone concentration as a covariate in our analyses related to metabolic changes pre- and post-leuprolide. Likewise, even though micronized estrogen and progesterone are optimized for oral absorption, if serum levels of estrogen and progesterone achieved are below the expected range observed in normal women, we will use these hormone concentrations as covariates in our statistical analyses. Although transdermal (patch or cream preparations) were an alternative to oral hormone therapy, the assessment of compliance with their use would have posed challenges. Pill counts, patient contact on a regular basis, and measurement of hormone levels in blood will be used to ensure and document use of study medication.

re: Specific Aim 3. This protocol requires high levels of commitment from study subjects who must use CPAP on a regular basis for the duration of the study. Compliance with CPAP use is automatically recorded and powering on the device can be differentiated from patient use via sensors incorporated into the CPAP mask. Thus, we will have device-generated compliance records.

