**Polysomnography**

Sleep recordings will be performed in the laboratory using a Nihon Kohden (Neurofax EEG- 1100A) digital EEG acquisition system. Recordings will include electroencephalography (EEG), electrooculography (EOG), electromyography (EMG), electrocardiography (EKG) signals and a chest belt to evaluate respiration. Full polysomnography will also include oronasal airflow by thermocouples, respiratory effort from thoracic and abdominal piezo electric belts, and pulse oximetry. Prior to study sessions, all subjects will undergo one night of full polysomnography to detect sleep disordered breathing (AHI > 15, no OSA is defined as AHI < 5) and to exclude periodic limb movement disorder (PLM arousal index > 1). This screening night will also serve as habituation night. During the experimental protocol, three nights will be recorded. Each 30-sec epoch of recording will be visually scored as stage Wake, I, II, III, IV or REM following standard criteria by an experienced rater who will be blinded to the age and gender of the subject and the study condition. Respiratory events, periodic limb movements and microarousals will be scored according to established criteria. Spectral analysis of sleep EEG will be performed using specially designed software (PRANA, PhiTools, Strasbourg, France) in the delta, theta, alpha, sigma, beta and gamma bands.

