- The GCRC nurses who perform these procedures are highly trained and thus the risks directly associated with intravenous puncture and blood withdrawal described above are minimal. For those subjects randomized to take pioglitazone, monitoring of hepatic function will be performed as described above. Subjects may choose not to participate in the study, and may discontinue the study at any time point. Conventional diagnostic and therapeutic modalities will be made available to all subjects where appropriate. In the event of physical injury resulting from this research, the University of Chicago Hospitals will provide emergency care at no cost to the subject, if such care is necessary. The University of Chicago Hospitals will also provide non-emergency care, but the Medical Center assumes no responsibility to pay for such care or to provide financial compensation. Confidentiality is always respected. Specimens are logged by number according to routine practices of the institution. Data collected are included in the patients' charts and results of the studies are made available to patients, their legal guardian, and their referring physicians. Samples are not available to any investigators other than those listed herein.

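### Aim 2 is labelled double-blind, but no rule keeps hormone results that would usually reveal the arm away from site staff, charts, patients and physicians

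*Combined protocol and SAP*

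**What the plan says.** The Specific Aims state that "subjects will be randomized in a double-blind placebo controlled fashion to one of two treatment arms for a period of six weeks". Section D3 (Detail of methods pertaining to Specific Aims 2 and 3) repeats the label: "one of two treatment regimens in a randomized, double-blind, placebo controlled fashion, for a period of 6 weeks". Each woman takes one active hormone, either 2 mg micronized estradiol plus placebo or "200 mg micronized progesterone (Prometrium®) plus placebo". Treatment starts six weeks after depot leuprolide, with which "there is prolonged (3 month) suppression of pituitary gonadotropin levels and ovarian steroid levels".

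For Aim 2, section D4 names pill counts and regular patient contact, and adds that "measurement of hormone levels in blood will be used to ensure and document use of study medication". It also compares the estrogen and progesterone levels reached with those of normal women, and makes them covariates if they fall short.

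Section E.1.c (Potential Risks) says: "Data collected are included in the patients' charts and results of the studies are made available to patients". The same sentence extends access to legal guardians and referring physicians.

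Two provisions limit the exposure. In section D5, the Polysomnography text has sleep stages scored by a rater "blinded to the age and gender of the subject and the study condition", and the blood-sampling text requires all of one woman's samples for a given hormone to be run in one assay.

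**The concern.** The hormones measured are the treatments compared. With ovarian production suppressed, the woman on estradiol should show estradiol and the woman on progesterone should show progesterone. Anyone who sees the result can probably name the arm.

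Using these levels to check compliance makes this worse. A low estradiol suggests missed tablets in one arm and correct treatment in the other, so compliance cannot be judged from the value without knowing or inferring the arm. The plan gives this task to no unblinded person, does not withhold the values from site staff, and does not say who holds the estrogen/progesterone code.

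What is at stake is the blind itself, which the plan claims for all 40 Aim 2 women. If assignments become known early, they could influence how staff handle compliance and drop-outs, self-reported sleepiness and mood, and any AHI scoring not yet done.

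**Working it through.** The plan states no figure on this point, so there is none to reproduce. The check has three steps.

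**1. When can a revealing value arise?**
- Section D3 (Statistical Considerations) gives Aim 2 three time points: T1 baseline, T2 six weeks after leuprolide, and T3 after six weeks of estrogen or progesterone.
- Table D1 lists estradiol, estrone and progesterone twice in each Aim 2 arm. This fits T2 and T3, with baseline covered under Aim 1. The table does not name the visits.
- No visit or draw is described between T2 and T3. T2 precedes the estrogen/progesterone randomisation, so the first scheduled value that can reveal the arm is at T3.
- The word *ensure* in D4 leaves room for an on-treatment level, but none is scheduled.

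**2. How revealing is one estradiol value?**
- From the plan: steady-state estradiol of about 220 pmol/L on 2 mg per day (D3, Detail of methods), and an assay sensitivity of 2.8 pg/ml for the GnRH agonist test (D5).
- Assay check: with an estradiol molar mass of 272.38 g/mol, 2.8 × 1000/272.38 = 10.3 pmol/L, and 220/10.3 ≈ 21. The assay would register the estradiol-arm level easily.
- Not in the plan: the suppressed estradiol level in the progesterone arm and the between-woman CV. Both are assumed, over a range.
- Model: log-normal levels, the same CV in both arms, equal arm sizes, and a cut midway on the log scale. With s = √ln(1 + CV²), the proportion classified correctly is Φ(ln(220/L)/(2s)), where L is the suppressed level.
- Example: L = 40 and CV = 50% give s = √ln 1.25 = 0.472, ln(220/40) = 1.705, 1.705/0.945 = 1.80, and Φ(1.80) = 0.964.

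| Assumed L (pmol/L) | CV 30% | CV 50% | CV 70% |
|---|---|---|---|
| 20 | >99.9% | 99.4% | 97.1% |
| 40 | 99.8% | 96.4% | 91.1% |
| 75 | 96.7% | 87.3% | 80.3% |
| 100 | 91.0% | 79.8% | 73.4% |

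Guessing gives 50%. Progesterone, read alongside, can only add information. The plan describes its expected level as late follicular to early luteal, without a number.

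**3. Do the existing safeguards close the gap?**
- The same-assay rule implies that 24-hour profile results for one woman appear only after her T3. It stands in the text on 24-hour sampling and is not described as a blinding measure. The separate text on assays for the GnRH agonist test does not repeat it, and it does not prevent a completed woman's results from circulating while others are on treatment.
- The blinded rater is named in the sentence on sleep staging. The next sentence, on respiratory events, does not repeat the blinding, and those events make up the AHI, the Aim 2 primary outcome.
- Neither rule limits who sees hormone results, and E.1.c sets no delay.

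**The case against.** The strongest reply is about timing. With no scheduled draw between T2 and T3 and one assay run per woman, a value read after T3 cannot change that woman's own retention, compliance or T3 questionnaires. Hormone levels would then only document use, while pill counts and contact do the work during treatment. This stands for scheduled samples. A reader might infer that women are unblinded during their own treatment, but the documents do not schedule the sample that this needs.

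Three other inferences are tempting and also unsupported:
- *Later assignments become guessable.* That needs small blocks. Section D3 states blocking for the 2:1 allocation between Aims 2 and 3, but for estrogen versus progesterone it mentions only random numbers from a computer.
- *The investigators expect progesterone to win.* The 50% versus 23% falls in AHI illustrate a detectable difference under a two-sided test. They are not a stated expectation.
- *The arm is revealed with certainty.* The suppressed level is not documented, and the lower rows of the table show how much depends on it.

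It is also fair to say that the paragraph in E.1.c refers to subjects randomised to pioglitazone, which is not a drug in this study, so it may be carried over from another protocol. It is still current text. Its silence on timing does not show early release, but nothing in the plan prevents it.

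**Conclusion.** The point holds in a limited form. The plan claims a double blind, measures the two treatments themselves as hormones, uses the levels for compliance, and sets no restriction or delay on who sees them. The main exposure is T3 results reaching site staff, charts, patients or physicians while Aim 2 is still running or before AHI scoring is locked. Any on-treatment level read in order to ensure use would add to it.

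An estradiol value would usually reveal the arm: about 91% to over 99% correct at assumed suppressed levels of 20 to 40 pmol/L, and 73% to 97% at 75 to 100 pmol/L, with CVs of 30% to 70%. These figures assume that tablets are taken and that 220 pmol/L is reached.

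The effect on AHI is probably small, since sleep staging is blinded and the same rater may well score respiratory events, though the plan does not say so. Neither this effect nor any effect on retention or self-reported outcomes can be sized from the documents. A reader might conclude that the Aim 2 comparison is invalid; the documents do not support that. The correction is still worth making, because it is nearly free and protects a property that the plan claims.

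**What to change.** - **D4, Aim 2:** rely on the pill counts and patient contact already planned for compliance during treatment, and use hormone levels only to document use afterwards.
- **Flow of results:** have the laboratory, itself without access to the randomisation schedule, send post-randomisation estradiol, estrone, progesterone, LH and FSH results only to the biostatistician. State that the biostatistician holds the estrogen/progesterone code and makes the D4 comparison with normal levels.
- **E.1.c:** exempt these results from charts and from release to site staff, patients and physicians until the last Aim 2 woman has completed T3 and AHI scoring is locked, with emergency unblinding available. Remove or explain the reference to pioglitazone in the same paragraph.
- **D5, Polysomnography:** state that respiratory-event scoring is also blinded to arm.

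The cost is a few sentences and a reporting restriction, with no added visit, sample or procedure. The downside is that patients receive these hormone results later.

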**D5. Methods of procedure****Wrist activity monitoring**

The Activwatch wrist activity monitor (Mini-Mitter Company, Inc., Sunriver, Oregon) is a miniature device (30 x 30 x 10 mm) that is accurate, sturdy and lightweight (< 68g including batteries). It has an extended memory capacity. Specially designed hardware and software for data downloading, graphing and analysis are available for this system. Wrist activity recordings will provide objective estimations of sleep duration for one week prior to the study.

**Polysomnography**

Sleep recordings will be performed in the laboratory using a Nihon Kohden (Neurofax EEG- 1100A) digital EEG acquisition system. Recordings will include electroencephalography (EEG), electrooculography (EOG), electromyography (EMG), electrocardiography (EKG) signals and a chest belt to evaluate respiration. Full polysomnography will also include oronasal airflow by thermocouples, respiratory effort from thoracic and abdominal piezo electric belts, and pulse oximetry. Prior to study sessions, all subjects will undergo one night of full polysomnography to detect sleep disordered breathing (AHI > 15, no OSA is defined as AHI < 5) and to exclude periodic limb movement disorder (PLM arousal index > 1). This screening night will also serve as habituation night. During the experimental protocol, three nights will be recorded. Each 30-sec epoch of recording will be visually scored as stage Wake, I, II, III, IV or REM following standard criteria by an experienced rater who will be blinded to the age and gender of the subject and the study condition. Respiratory events, periodic limb movements and microarousals will be scored according to established criteria. Spectral analysis of sleep EEG will be performed using specially designed software (PRANA, PhiTools, Strasbourg, France) in the delta, theta, alpha, sigma, beta and gamma bands.

**Sleep questionnaires**

The *Pittsburgh Sleep Quality Index (PSQI)*. This index is derived from a self-rated 21 item questionnaire that assesses sleep quality and disturbances over a 1 month time interval. Seven "component" scores

ranging from 0 to 3 for each component are generated from this survey; one global score (PSQI) is derived from the sum of these seven scores. A global PSQI score greater than 5 has a diagnostic sensitivity of 89.6% and specificity of 86.5% in distinguishing good and poor sleepers. The seven components include: subjective sleep quality, sleep latency, sleep duration, habitual sleep efficiency, sleep disturbances, use of sleeping medication, and daytime dysfunction.

*The Berlin Questionnaire.* This questionnaire is used to assess risk for sleep apnea through questions regarding risk factors – snoring behavior, wake time sleepiness or fatigue, and the presence of obesity or hypertension. This instrument predicts high risk for sleep apnea (an RDI of 5 or greater) with a sensitivity of 0.86, specificity or 0.77, a positive predictive value of 0.89, and a likelihood ratio of 3.2.

*The Epworth Sleepiness Scale (ESS).* This survey was used to assess the level of chronic daytime sleepiness. A score of 10 or greater is indicative of excessive daytime sleepiness.

